## 6.2. Primary and Supportive Estimands

There will be 3 estimands of interest in analyzing primary and major secondary endpoints for the Double-Blinded Treatment Period. Two types of intercurrent events (ICEs) in terms of estimating the treatment effects for the treatment period will be considered: Initiation of rescue medication as defined in [Appendix 2](#) and permanent treatment discontinuation.

### 6.2.1. Primary Estimand (Hybrid)

The primary estimand is a hybrid estimand representing the primary clinical question of interest: What is the difference between treatment conditions (that is, lebrikizumab vs placebo) in the target patient population in successful responses or means after 16 weeks achieved without use of rescue medication, and if all patients continued with treatment except those who discontinued due to lack of efficacy?

The primary estimand is described by the following attributes:

- Population: Defined through appropriate inclusion/exclusion criteria to reflect the targeted patient population for approval
- Endpoint: Apply to all primary and major secondary endpoints
- How to account for ICEs
  - Subjects who require any use of rescue medication or discontinued treatment due to lack of efficacy prior to Week 16 will be considered as treatment failures, that is, nonresponder, after the ICEs. Therefore, composite strategy is used for these types of ICEs.
  - For subjects who discontinue treatment due to reasons other than lack of efficacy prior to Week 16, a hypothetical strategy will be used to estimate what the treatment effect would have been if subjects continued with treatment. Therefore, hypothetical strategy is used for these types of ICEs.
- Population-level summary: Difference in response proportions or means between treatment conditions.

### 6.2.2. Supportive Estimand for Categorical Endpoints (Composite)

The supportive estimand for categorical endpoints is a composite estimand representing the supportive clinical question of interest: What is the difference between treatment conditions in the target patient population in successful responses after 16 weeks achieved without use of rescue medication or treatment discontinuation?

The supportive estimand is described by the following attributes:

- Population: Defined through appropriate inclusion/exclusion criteria to reflect the targeted patient population for approval
- Endpoint: Apply to categorical endpoints
- How to account for ICEs
  - Subjects who require any use of rescue medication or discontinued treatment prior to Week 16 will be considered as treatment failures, that is, nonresponders, after the ICEs. Therefore, composite strategy is used for these types of ICEs.
- Population-level summary: Difference in response proportions between treatment conditions.

**6.2.3. Supportive Estimand for Continuous Endpoints (Hypothetical)**

The supportive estimand for continuous endpoints is a hypothetical estimand representing the supportive clinical question of interest: What is the difference between treatment conditions in the target patient population in means after 16 weeks if rescue medication was not available and all patients adhered to the treatment?

The supportive estimand is described by the following attributes:

- A. Population: Defined through appropriate inclusion/exclusion criteria to reflect the targeted patient population for approval
- B. Endpoint: Apply to continuous endpoints
- C. How to account for ICEs
  - For subjects who require any use of rescue medication or discontinued treatment prior to Week 16, a hypothetical strategy will be used to estimate what the treatment effect would have been if rescue medication was not available and all subjects adhered to the treatment. Therefore, hypothetical strategy is used for these types of ICEs.
- Population-level summary: Difference in means between treatment conditions.

Analytical details of the primary and secondary analyses are available in Sections 6.4 and 6.11.

Table KGAD.6.3 summarizes different analyses that will be conducted on the 3 estimands.

**Table KGAD.6.3. Description of Primary and Supportive Estimands**

Estimand	Analysis Strategy for Intercurrent Events			Missing Data Imputation Method
	Rescue Medication	Treatment Discontinuation		
		Due to Lack of Efficacy	Due to Any Other Reasons	
Primary Estimand (Hybrid)	Composite: Set to baseline	Composite: Set to baseline	Hypothetical: Set to missing	Primary analysis: MCMC-MI Sensitivity analysis: Tipping point analysis
Supportive Estimand for	Composite:	Composite:	Composite:	NRI

Categorical Endpoints (Composite)	Set to nonresponder	Set to nonresponder	Set to nonresponder	
Supportive Estimand for Continuous Endpoints (Hypothetical)	Hypothetical: Set to missing	Hypothetical: Set to missing	Hypothetical: Set to missing	MMRM, LOCF

Abbreviations: LOCF = last observation carried forward; MCMC-MI = Markov chain Monte Carlo multiple imputation; MMRM = mixed-model repeated measures; NRI = nonresponder imputation.

### 6.3. Adjustments for Covariates

Unless otherwise specified, the statistical analysis models for the Treatment Period efficacy and health outcome analysis will include the following stratification factors for Baseline randomization: geographic region (US versus EU versus rest of world), age group (adolescent patients 12 to <18 versus adults  $\geq 18$  years) and baseline disease severity (IGA 3 versus 4).

Below are the country allocations within each geographic region.

**Table KGAD.6.4. Geographic Regions for Statistical Analysis**

Geographic Region	Country or Countries
US	US
Europe	Germany, Poland
Rest of world	Canada

In general, when an MMRM is to be used for analyses, baseline value and baseline-by-visit interactions will be included as covariates; when an ANCOVA is to be used for analyses, baseline value will be included as a covariate.

### 6.4. Handling of Dropouts or Missing Data

Depending on the estimands being addressed, different methods will be used to handle missing data. Description of the estimands can be found in Section 6.2.

For efficacy analysis relative to the primary estimand, the primary method of handling missing data including those as a result of ICEs will be based on Markov Chain Monte Carlo multiple imputation (MCMC-MI). The description of the MCMC-MI method can be found in Section 6.4.1. Tipping point analysis as described in Section 6.4.2 will serve as the sensitivity analysis for the primary analysis.

For efficacy analysis relative to the supportive estimand for categorical endpoints, missing data including those as a result of ICEs will be imputed as nonresponder. The description of nonresponder imputation (NRI) can be found in Section 6.4.3.

For efficacy analysis relative to the supportive estimand for continuous endpoints collected only once postbaseline, missing data including those as a result of ICEs will be imputed using LOCF. The description of LOCF can be found in Section 6.4.4.

For efficacy analysis relative to the supportive estimand for continuous endpoints collected multiple times postbaseline, an MMRM will be performed without explicit imputation. The description of MMRM can be found in Section [6.4.5](#).

[Table KGAD.6.5](#) describes the planned imputation methods for efficacy and health outcome endpoints for the Double-Blinded Treatment Period.

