**Table KGAD.6.5. Imputation Techniques for Various Variables During Double-Blinded Treatment Period**

Type of Endpoints	Efficacy and Health Outcome Endpoints	Estimand (Analysis Strategy for Intercurrent Events)	Missing Data Imputation Method (Analysis Method)
Categorical	IGA, EASI, Pruritus NRS, DLQI, and Sleep-loss related categorical endpoints at prespecified timepoints	Primary Estimand (Hybrid)	MCMC-MI, Tipping point analysis (CMH)
		Supportive Estimand (Composite)	NRI (CMH)
	Remaining categorical endpoints	Supportive Estimand (Composite)	NRI (CMH)
Continuous	EASI percent change, Pruritus NRS percent change, Sleep-loss change from Baseline, and DLQI change from Baseline	Primary Estimand (Hybrid)	MCMC-MI (ANCOVA)
		Supportive Estimand (Hypothetical)	No imputation (MMRM)
	Remaining continuous endpoints collected at multiple postbaseline timepoints including BSA, POEM, and CDLQI	Supportive Estimand (Hypothetical)	No imputation (MMRM)
	Remaining continuous endpoints collected only once postbaseline	Supportive Estimand (Hypothetical)	LOCF (ANCOVA)

Abbreviations: ANCOVA = analysis of covariance; BSA = body surface area; CDLQI = Children's Dermatology Life Quality Index; CMH = Cochran-Mantel-Haenszel; DLQI = Dermatology Life Quality Index; EASI = Eczema Area and Severity Index; IGA = Investigator's Global Assessment; LOCF = last observation carried forward; MCMC-MI = Markov chain Monte Carlo multiple imputation; MMRM = mixed-model repeated measures; NRI = nonresponder imputation; NRS = Numeric Rating Scale; POEM = Patient-Oriented Eczema Measure.

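### SCORAD, EQ-5D, PROMIS and ACQ-5 change scores are assigned a hypothetical estimand, but the LOCF rule gives rescued patients zero change, which is in effect a composite rule

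*SAP*

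**What the plan says.** - **Estimand.** SAP 6.2.3 asks for the difference "in means after 16 weeks if rescue medication was not available and all patients adhered to the treatment". SAP 6.2 introduces the estimands for a narrower set: "There will be 3 estimands of interest in analyzing primary and major secondary endpoints". Table KGAD.6.5 extends this one to two further groups: "Remaining continuous endpoints collected only once postbaseline", with LOCF and ANCOVA, and "Remaining continuous endpoints collected at multiple postbaseline timepoints including BSA, POEM, and CDLQI", with MMRM.
- **Method.** SAP 6.4 says that for "continuous endpoints collected only once postbaseline, missing data including those as a result of ICEs will be imputed using LOCF". Table KGAD.6.9 plans only ANCOVA with LOCF for the SCORAD, EQ-5D, PROMIS and ACQ-5 change scores.
- **Rule.** SAP 6.4.4 deletes values after rescue or treatment discontinuation, carries the last value forward, and uses baseline when nothing postbaseline is available.
- **Table KGAD.6.3.** The continuous supportive row reads "Hypothetical: Set to missing" for every intercurrent event and lists MMRM and LOCF as methods. The primary-estimand row reads "Composite: Set to baseline" for rescue.
- **Stated assumption.** SAP 6.4.5 names MAR for the MMRM. SAP 6.4.4 names no assumption for LOCF.
- **Schedule.** Protocol 7.2 to 7.12 and Appendix 1 place all four instruments at Baseline and Week 16/ET only. Protocol 7.13 asks for IGA, BSA and EASI at unscheduled visits for an AD exacerbation. Under protocol 6.4, rescued patients stay in follow-up and continue to be assessed.

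**The concern.** With a single planned postbaseline assessment, carrying the last observation forward after rescue means carrying baseline forward. The Week 16 value of a rescued patient is collected, deleted and replaced by baseline. The SAP presents the result as an estimate of what would have happened without rescue, yet gives no reason why that outcome would be no change.

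Within one estimand, the same rescued patient is treated as unchanged on SCORAD but as MAR on POEM and BSA. The two sets of results would appear under one label and answer different questions. What is at stake is the meaning of these supportive results. No primary or major secondary conclusion depends on them.

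**Working it through.** **Step 1: trace one rescued patient.** The patient starts rescue at, say, Week 6 and attends Week 16.

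| Endpoint | Values before rescue | Week 16 value | What enters the analysis |
|---|---|---|---|
| SCORAD, EQ-5D, PROMIS, ACQ-5 | Baseline only | Deleted (6.4.4) | Baseline, so change = 0 |
| BSA, POEM | Baseline and earlier visits | Deleted (6.4.5) | Earlier values, remainder MAR |
| EASI, primary estimand | Baseline and earlier visits | Replaced (6.4.1) | Baseline, labelled composite |

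The first and third rows give the same Week 16 number under different labels. The first two share a label but not an assumption.

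**Step 2: when zero-filling hits the target.** Let m be the arm mean change without rescue, d the share of event patients, and r their change without the event as a fraction of m. Subscripts are L (lebrikizumab) and P (placebo), and k = mP/mL. If every event patient gets baseline, the arm mean is m(1 − d·r). Hence

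relative error of the difference = (k·dP·rP − dL·rL)/(1 − k).

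It is zero if rL = rP = 0 (event patients would not have changed), or if k·dP·rP = dL·rL (the arm errors cancel).

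**Step 3: illustrative size.** The documents give no means or event rates for these scales, so every input here is assumed. With mean changes of −60 and −40 points and r = 1, the true difference is −20:

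- Events 5% vs 15%: 0.95 × (−60) − 0.85 × (−40) = −57 + 34 = −23.
- Events 15% vs 15%: 0.85 × (−60) − 0.85 × (−40) = −51 + 34 = −17.
- No true difference (both −40), events 10% vs 30%: −36 + 28 = −8.

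**Step 4: would MAR imputation do better?** If the predictors carry no information, imputation reproduces the mean of the event-free patients, m(1 − d·r)/(1 − d). The arm error is then m·d(1 − r)/(1 − d). This is the least favourable case for imputation. With k = 2/3, relative errors (+ means too large) are:

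| (rL, rP) | 10% vs 25%: LOCF | 10% vs 25%: MAR imputation | 10% vs 10%: LOCF | 10% vs 10%: MAR imputation |
|---|---|---|---|---|
| (1, 1) | +20% | 0 | −10% | 0 |
| (0.5, 0.5) | +10% | −16.7% | −5% | +5.6% |
| (0, 0) | 0 | −33.3% | 0 | +11.1% |
| (1, 0.25) | −17.5% | −50% | −25% | −16.7% |

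Example, 10% vs 25% with r = 0. LOCF: (0 − 0)/(1/3) = 0. Imputation: 1/0.9 − (2/3)/0.75 = 0.222 against a true 0.333, which is 33% too small.

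Informative predictors shrink the imputation error. In a simulation with assumed mean changes of −30 and −20, SD 18, a mid-study score correlated 0.7 with the outcome, and events depending on that score (11% vs 24%), LOCF was 7.7% too large under MAR and imputation was within 0.1%. When event patients did 5 points worse than MAR predicts, LOCF was 1.2% too large and imputation 5.9% too small. Neither method is closer in every case.

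**The case against.** - **The rule is disclosed and was chosen before unblinding.** This is true of the mechanics. The revision history shows that SAP Version 2 moved these four change scores to ANCOVA with LOCF. With one postbaseline value, the planned MMRM has no earlier value of the same scale to use. What remains missing is the link from the rule to the 6.2.3 question.
- **Zero change may be a fair guess for SCORAD.** Protocol 6.4 reserves rescue for intolerable worsening, so little improvement without it is plausible, and at r = 0 LOCF has no error. This stands as a reason to keep LOCF. It does not make the analysis hypothetical.
- **A reader might infer that LOCF should be replaced by multiple imputation.** The documents do not support that. Step 4 shows imputation further off in several cases. The MAR assumption in 6.4.5 rests on repeated measurements of the same endpoint, so imputing SCORAD or PROMIS from other instruments would be a new assumption. For ACQ-5, protocol 6.1 counts systemic corticosteroids for an asthma exacerbation as rescue. Zero change may flatter that patient, and MAR in an improving arm would flatter the patient more.
- **A reader might infer that LOCF favours lebrikizumab.** Steps 3 and 4 show errors in both directions, and all of them depend on assumed inputs.
- **A reader might infer that Table KGAD.6.3 itself calls this row composite, or that all discontinuers also get zero.** The table labels the row hypothetical. For discontinuers, 6.4.4 does not say whether the ET value counts as falling after discontinuation. The paragraph in 6.1.2 on variables not collected at every visit keeps unscheduled assessments for LOCF, which may point to carrying it forward. If so, d in Step 2 covers fewer patients.

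**Conclusion.** The mismatch between estimand and estimator is established from the text and needs no assumed figures. A patient rescued before the only planned postbaseline assessment is scored as unchanged, while the SAP labels the result as the effect without rescue. The label should change, and the strategy for discontinuers should be made explicit.

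The size of any bias cannot be derived from the documents. The assumed inputs in Step 4 give LOCF errors from −25% to +20% of the true difference, and zero if rescued patients would not have changed.

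The reach is limited to change scores listed among the other efficacy endpoints, outside both the US and EU testing schemes. The nonresponder analyses of SCORAD75/90 and of the EQ-5D domains are not affected. This is worth correcting but does not threaten the trial's main conclusions.

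**What to change.** 1. Keep ANCOVA with LOCF for the SCORAD, EQ-5D, PROMIS and ACQ-5 change scores. In SAP 6.2.3, 6.4 and Tables KGAD.6.3, 6.5 and 6.9, define it as a composite, set-to-baseline strategy for rescue, and do not report it as a hypothetical effect. A definition is needed because 6.2.2 says "Endpoint: Apply to categorical endpoints".
2. In 6.4.4, state whether a discontinuer's ET value is carried forward, consistently with 6.1.2, and name the discontinuation strategy to match.
3. If the hypothetical effect is still wanted, add a supplementary analysis beside LOCF: within-arm multiple imputation under a stated MAR assumption, with the existing 6.4.1 procedure (25 data sets). Use baseline and pre-event IGA, EASI, pruritus and sleep-loss scores as predictors. Add one delta-adjusted run in which event patients do worse than MAR predicts. For ACQ-5, justify the model separately or omit it, because skin scores may predict asthma control weakly.

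Cost: items 1 and 2 are text edits. Item 3 needs six imputation models (SCORAD, EQ-5D VAS, UK index, US index, PROMIS anxiety, PROMIS depression), or seven with ACQ-5, and one seed per arm for each: 12 or 14 seeds. Any of this is a documented change after SAP Version 4, which itself followed primary database lock. Statisticians blinded to the data should make it, and the CSR should describe it.

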**Table KGAD.6.5. Imputation Techniques for Various Variables During Double-Blinded Treatment Period**

Type of Endpoints	Efficacy and Health Outcome Endpoints	Estimand (Analysis Strategy for Intercurrent Events)	Missing Data Imputation Method (Analysis Method)
Categorical	IGA, EASI, Pruritus NRS, DLQI, and Sleep-loss related categorical endpoints at prespecified timepoints	Primary Estimand (Hybrid)	MCMC-MI, Tipping point analysis (CMH)
		Supportive Estimand (Composite)	NRI (CMH)
	Remaining categorical endpoints	Supportive Estimand (Composite)	NRI (CMH)
Continuous	EASI percent change, Pruritus NRS percent change, Sleep-loss change from Baseline, and DLQI change from Baseline	Primary Estimand (Hybrid)	MCMC-MI (ANCOVA)
		Supportive Estimand (Hypothetical)	No imputation (MMRM)
	Remaining continuous endpoints collected at multiple postbaseline timepoints including BSA, POEM, and CDLQI	Supportive Estimand (Hypothetical)	No imputation (MMRM)
	Remaining continuous endpoints collected only once postbaseline	Supportive Estimand (Hypothetical)	LOCF (ANCOVA)

Abbreviations: ANCOVA = analysis of covariance; BSA = body surface area; CDLQI = Children's Dermatology Life Quality Index; CMH = Cochran-Mantel-Haenszel; DLQI = Dermatology Life Quality Index; EASI = Eczema Area and Severity Index; IGA = Investigator's Global Assessment; LOCF = last observation carried forward; MCMC-MI = Markov chain Monte Carlo multiple imputation; MMRM = mixed-model repeated measures; NRI = nonresponder imputation; NRS = Numeric Rating Scale; POEM = Patient-Oriented Eczema Measure.

#### **6.4.1. Primary Analysis - Markov Chain Monte Carlo Multiple Imputation (MCMC-MI)**

The primary method of handling missing efficacy data relative to the primary estimand will be as follows for both binary and continuous endpoints:

For patients who receive rescue medication (high-potency TCS or systemic AD treatment, defined in [Appendix 2](#)) or discontinue treatment due to lack of efficacy, set to the patient's baseline value subsequent to this time through Week 16. The MCMC-MI will be used to handle the remaining missing data. Imputation will be conducted within each treatment group independently so the pattern of missing observations in one treatment group cannot influence missing value estimations in another. The SAS PROC MI with the MCMC option will be used to conduct the MCMC-MI. The imputation model will include the relevant baseline and postbaseline.

For each imputation process, 25 datasets with imputations will be calculated. The initial seed values are given in [Table KGAD.6.6](#). Each complete data set will be analyzed with the specified analysis. The results from these analyses will be combined into a single inference using SAS PROC MIANALYZE.

Cochran-Mantel-Haenszel (CMH) test statistic will be transformed using the Wilson-Hilferty transformation and then standardized (Ratitch 2013) prior to combining them using SAS PROC MIANALYZE. Details of combining estimates and test statistics for categorical endpoints with multiple imputation can be found in [Appendix 3](#).

For binary responses related to EASI and IGA, the binary response variables will be calculated based on the multiply imputed datasets that have been created. Because the MCMC algorithm is based on the multivariate normal model, imputed values for IGA will not generally be one of the discrete values used in IGA scoring (0, 1, 2, 3, or 4). Therefore, to derive the binary IGA response variable, standard rounding rules will be applied to the imputed values. For example, if a patient has an IGA score imputed as 1.4 (and assuming a Baseline IGA score of 3), the imputed value would be rounded down to 1, and the minimum change from Baseline of 2 would have been met. This patient would be considered a responder.

For derivation of an EASI-75 and EASI-90 response, no rounding will be performed. The imputed Week 16 EASI value will be compared directly to the observed Baseline EASI value to determine whether a reduction of at least 75% or 90% was achieved.

For derivation of the following Pruritus NRS responses, no rounding will be performed. The imputed Pruritus NRS value will be compared directly to the observed mean baseline Pruritus NRS value to determine whether a response was achieved:

- Percentage of patients with a Pruritus NRS of  $\geq 4$ -points at Baseline who achieve a  $\geq 4$ -point reduction from Baseline to Weeks 1, 2, 4, and 16.

Imputation of continuous data will parallel that of binary variables. The imputed values will be used for the following secondary endpoints:

- Percentage change in Pruritus NRS score from Baseline to Week 16.
- Percentage change in EASI score from Baseline to Week 16.

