**Figure KGAD.5.1. Illustration of study design for Clinical Protocol KGAD.**

## 5.2. Determination of Sample Size

For FDA: Approximately 225 patients will be randomized at a 2:1 ratio to lebrikizumab or placebo (150 patients:75 patients). The assumed IGA score of 0 or 1 at Week 16 response rates are 38% for lebrikizumab 250 mg Q2W and 13% for placebo. The assumption for lebrikizumab is based on the DRM06-AD01 Phase 2b study, the proportion of patients who achieved an IGA score of 0 or 1 at Week 16 using the rescue medication non-response sensitivity analysis, adjusting for the allowed use of TCS/topical calcineurin inhibitors (TCI). The placebo response rates are based on the review of historical TCS clinical studies in AD. This study has power >95% for testing superiority of lebrikizumab to placebo based on a two-sided Fisher's exact test with alpha of 0.05.

For European Medicines Agency (EMA): Approximately 225 patients will be randomized at a 2:1 ratio to lebrikizumab or placebo (150 patients:75 patients). The assumed IGA score of 0 or 1 at Week 16 response rates are 38% for lebrikizumab 250 mg Q2W and 13% for placebo. The assumed Eczema Area and Severity Index (EASI) 75 response rate at Week 16 response rates are 58% for lebrikizumab 250 mg Q2W and 20% for placebo. The assumptions for lebrikizumab are based on the DRM06-AD01 Phase 2b study, the proportion of patients who achieved an IGA score of 0 or 1 and proportion of patients who achieved EASI75 response at Week 16 using the rescue medication non-response sensitivity analysis, adjusting for the allowed use of TCS/TCI. The placebo response rates are based on the review of historical TCS clinical studies in atopic dermatitis. This study has power >95% for testing superiority of lebrikizumab to placebo based on a two-sided Fisher's exact test with alpha of 0.05.

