### **6.11. Efficacy Analyses**

[Table KGAD.6.8](#) includes the description and derivation of the efficacy/health outcomes measures and endpoints. [Table KGAD.6.9](#) provides the detailed analyses including analysis type, method and imputation, population, time point, and treatment comparisons for efficacy/health outcomes analyses.

Table KGAD.6.8. Description and Derivation of Efficacy/Health Outcomes Measures and Endpoints

Measure	Description	Variable	Derivation / Comment	Imputation Approach if Missing Components
Investigator's Global Assessment (IGA)	The IGA is a static assessment and rates the severity of the patient's AD. The IGA is comprised of a 5-point scale ranging from 0 (clear) to 4 (severe) and a score is selected using descriptors that best describe the overall appearance of the lesions at a given time point.	IGA score	Single item. Range: 0 to 4 0 represents "clear" 4 represents "severe"	Single item, missing if missing.
		Change from baseline in IGA score	Change from baseline: observed IGA score – baseline IGA score	Missing if baseline or observed value is missing.
		
 
▪ IGA [0,1] with <math>\geq 2</math>-point improvement
 
▪ IGA [0]
 
	
 
▪ Observed score of 0 or 1 and change from baseline <math>\leq -2</math>
 
▪ Observed score of 0
 
	
 
▪ Missing if baseline or observed value is missing.
 
▪ Single item, missing if missing.
 

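### Imputed IGA values are rounded without being bounded to the 0–4 scale, so the scoring of a draw below −0.5 on the primary endpoint is left open and, applied literally, is a nonresponse

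*SAP*

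**What the plan says.** SAP 6.4.1 first sets patients who used rescue medication, or who stopped treatment for lack of efficacy, to their baseline value. After that, "The MCMC-MI will be used to handle the remaining missing data". On the tool it says: "The SAS PROC MI with the MCMC option will be used to conduct the MCMC-MI". It acknowledges that the model is multivariate normal and that "imputed values for IGA will not generally be one of the discrete values used in IGA scoring (0, 1, 2, 3, or 4"). Its remedy is that "standard rounding rules will be applied to the imputed values", and the only worked example is a draw of 1.4 becoming 1. Protocol 9.3 has the same rule and the same example.

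In SAP 6.11, Table KGAD.6.8 describes the IGA as "Single item. Range: 0 to 4" and defines response as "Observed score of 0 or 1 and change from baseline" of −2 or lower.

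Neither SAP 6.4.1, Table KGAD.6.6, Table KGAD.6.8, Appendix 3 nor protocol 9.3 sets a minimum or maximum for the draws, truncates the rounded values, or says how a negative rounded value is scored.

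**The concern.** A normal model can return values below zero. A draw of −0.6 rounds to −1, which easily meets the change criterion but is neither 0 nor 1. If the two rules are programmed exactly as written, the most favourable draws are scored as failures.

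The gap is specific to IGA and works in one direction. EASI-75, EASI-90 and the pruritus response compare unrounded values with a one-sided threshold, so a negative draw still counts as a response. IGA draws above 4 do no harm, since they are nonresponses either way. Draws below −0.5 should be more common on the arm with lower IGA scores, so the expected bias is against lebrikizumab.

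The rule feeds the primary endpoint for both agencies, IGA response by visit, the IGA component of the composite with Pruritus NRS, and the subgroup analyses in SAP 6.15.1. Two programmers using the same seeds from Table KGAD.6.6 could both claim to follow the plan and still report different primary results.

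**Working it through.** **Inputs from the documents.** SAP 5.2 assumes that IGA 0/1 "response rates are 38% for lebrikizumab 250 mg Q2W and 13% for placebo", with 150 and 75 patients, a two-sided Fisher's exact test at 0.05, and power above 95%. SAP 6.4.1 specifies that "25 datasets with imputations will be calculated". Protocol 4.1 requires baseline IGA of at least 3, so any score of 1 or less is automatically a fall of at least 2 points.

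**Assumptions.** The documents give neither an SD for Week 16 IGA nor the share of Week 16 values that will be imputed. I vary the SD from 0.8 to 1.4 and the imputed share from 5% to 20%.

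**Step 1: the plan's own figure.** Exact enumeration of Fisher's test, 38% of 150 against 13% of 75, gives power of 98.4%. This agrees with the stated figure of more than 95%.

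**Step 2: share of draws lost.** Let an imputed value X be normal, with its mean chosen so that P(X < 1.5) equals the planned response rate r. Then mean = 1.5 − SD × z(r), and P(X < −0.5) = Φ(z(r) − 2/SD), where z(0.38) ≈ −0.31 and z(0.13) ≈ −1.13.

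| SD | Lebrikizumab: mean | Draws below −0.5 | As share of imputed responders | Placebo: mean | Draws below −0.5 |
|---|---|---|---|---|---|
| 0.8 | 1.74 | 0.25% | 0.7% | 2.40 | 0.01% |
| 1.0 | 1.81 | 1.1% | 2.8% | 2.63 | 0.09% |
| 1.2 | 1.87 | 2.4% | 6.4% | 2.85 | 0.26% |
| 1.4 | 1.93 | 4.2% | 11% | 3.08 | 0.53% |

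**Step 3: effect on the arm rate** (imputed share × share of draws lost).
- Smallest case, lebrikizumab: 5% × 0.25% ≈ 0.01 percentage points.
- Largest case, lebrikizumab: 20% × 4.15% ≈ 0.8 points, about 1.2 patients in 150.
- Largest case, placebo: 20% × 0.53% ≈ 0.1 points.

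**Step 4: simulation check.** Eight correlated visits were simulated with scores rounded to 0–4. The Week 16 value was removed at random in 10% of patients and imputed 25 times by normal regression on the first five visits, using fitted coefficients without redrawing them. SDs were 1.0 and 1.2, and visit-to-visit correlations 0.7 and 0.85. Scoring as a member of {0, 1} was compared with scoring as ≤1.
- Lebrikizumab lost 1.2% to 2.4% of imputed values, or 0.1 to 0.24 points on the arm rate (at most 0.36 of a patient in 150).
- Placebo lost 0.2% to 0.5%, or 0.02 to 0.05 points. At SD 1.2 the simulated placebo response was about 18%, above the planned 13%, so the upper placebo figure is generous.

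**Step 5: power.** Lowering the lebrikizumab rate by the largest amount in Step 3 gives about 37.2%. At 37.0% against 13%, exact Fisher power is 97.6%, so power stays at or above that over the whole range, against 98.4% with the fix. This treats the shifted rate as a single complete dataset and ignores imputation variance.

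**Step 6: individual patients.** The loss can be larger for a patient doing well when data stop. A predicted Week 16 IGA of 0.5 with residual SD 0.5 to 0.9 puts 2% to 13% of draws below −0.5. A predicted IGA of 0 puts 16% to 29% there.

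**The case against.** The strongest reply is that rounding is introduced precisely to bring draws back to the five scale values, that the scale is stated as 0 to 4, and that −1 is not on it. On that reading, mapping −1 to 0 is what any sensible programmer would do. Moreover, the response definition in Table KGAD.6.8 speaks of an observed score, not an imputed one. Much of this stands. A reader might infer that the plan scores these patients as nonresponders, or that the reported primary result is wrong. The documents support neither: no section says that −1 is a nonresponse, and a program coded as IGA ≤1, or with bounds set in the imputation step, would never meet the problem. What remains is that the stated rules, taken together and literally, give the wrong answer, and nothing in the text overrides them.

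A reader might also infer a bigger effect. At 10% missing, a loss of about 0.8 points needs essentially every missing lebrikizumab patient to be predicted near clear: 10% × 7.7% for a predicted IGA of 0.5 and residual SD 0.7. Setting rescue and lack-of-efficacy cases to baseline first does remove poor responders from the imputed group, but nothing in the documents shows so extreme a mix.

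Finally, the NRI analysis (SAP 6.4.3) and the tipping point analysis (SAP 6.4.2) do not use rounded draws, and the latter spans far larger shifts. That is true and reassuring for the conclusion, but neither analysis corrects the primary estimate or would reveal the anomaly.

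**Conclusion.** The point holds as an open specification with a small effect. Read literally, SAP 6.4.1 and Table KGAD.6.8 mis-score the best imputed IGA outcomes, on IGA only and in one direction. The likely cost is a few tenths of a percentage point on the lebrikizumab rate, with about 0.8 points at the edge of the assumed range and at most about 0.1 on placebo. These sizes rest on an assumed SD, an assumed imputed share and response rates matched to the planning values. The expected bias is against lebrikizumab, so it does not favour a false claim of efficacy, and over this range it does not threaten the stated power. The documents do not show which rule was programmed.

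**What to change.** In SAP 6.4.1, state that rounded imputed IGA values are truncated to 0–4 before response is derived. Equivalently, define imputed response as rounded IGA ≤1 with a fall of at least 2 points. Apply the same rule to the IGA component of the IGA and pruritus composite, and align protocol 9.3.

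The drafting and coding cost is about one line, but the timing carries a small cost. SAP section 3 records that Version 4 was written after primary database lock, when a limited number of study statisticians had been unblinded. A scoring change at that stage, in a direction expected to favour lebrikizumab, needs a stated reason. The sponsor should therefore confirm which rule the primary program used and record the clarification and its justification in the CSR. SAP 6.1 already provides for this when a method described in the protocol changes without altering a principal feature. The clarification leaves the endpoint and the estimand as they are.
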